If the patient died, the report should include the cause of death as the event term (with death as outcome) and whether or not the event leading to death was related to study intervention treatment, as well as the autopsy findings if available.

Do not delay reporting a suspected serious adverse event in order to obtain additional information. Any additional information, if collected, can be reported as a follow-up to the initial report. All serious adverse events that are either unexpected and possibly related or expected serious adverse events that are assessed as potential risks (Section 2.3) and adjudicated MACE events (or those suspect MACE events pending adjudication) will be followed until resolution, stabilization, the event is otherwise explained, or the patient is lost to follow-up.

Protocol Amendment 2

All serious adverse events continuing at the completion of the study must be assessed or followed to determine outcome.

APPENDIX 3. CONTRACEPTIVE GUIDANCE AND COLLECTION OF PREGNANCY INFORMATION

Advise male patients with female partners of reproductive potential to use effective contraception during treatment and for 2 weeks after the last dose of relugolix ([ORGOVYX \(relugolix\) USPI 2023](#)).

Male patients with partners who become pregnant

- The clinical research organization or investigator will attempt to collect pregnancy information on any male patient's female partner who becomes pregnant while the male patient is in this study. This applies only to male patients who receive relugolix.
- The investigator is to report a female partner pregnancy to the CRO within 8 calendar days of awareness and the CRO is to report a female partner pregnancy to the sponsor within 5 calendar days of awareness.
- After the necessary signed release of information form from the pregnant female partner is obtained, the clinical research organization or investigator will record additional pregnancy information on the appropriate form and the CRO will submit it to the sponsor within 5 days of receipt of the information. The female partner will also be followed to determine the outcome of the pregnancy. Information on the status of the mother and child will be forwarded to the sponsor. Generally, the follow-up will be no longer than 6 to 8 weeks following the estimated delivery date. Any termination of the pregnancy will be reported regardless of fetal status (presence or absence of anomalies) or indication for the procedure.

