7.4. Patient and Study Completion

For an individual patient, study completion is defined as their last study communication at the end of the study (including any follow-up visits or telephone contact for determination of resolution of an adverse event).

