8.3.5. Pregnancy in Female Partners of Male Patients

The male patient should report a pregnancy in his female partner.

Details of all partner pregnancies in female partners who become pregnant (estimated date of conception) during the study or within 2 weeks after the last dose of relugolix 120 mg or 3 months after the last dose of leuprolide acetate 22.5 mg 3-M or 6 months after the last 45 mg 6-M depot injection will be collected after the start of study intervention if the female partner agrees to provide information through a Release of Information form.

If a partner pregnancy is reported, the investigator should inform the sponsor (or designee) within 8 calendar days of learning of the pregnancy and should follow the procedures outlined in [Appendix 3](#).

Protocol Amendment 2

Abnormal pregnancy outcomes (eg, spontaneous abortion, fetal death, stillbirth, congenital anomalies, ectopic pregnancy) are considered serious adverse events.

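### Protocol Section 8.3.5 collects partner pregnancies in both arms, but the first bullet of Appendix 3, to which it sends the investigator, limits the attempt to collect information to relugolix patients

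*Protocol*

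**What the plan says.** Protocol Section 8.3.5 sets the scope of collection: "Details of all partner pregnancies in female partners who become pregnant (estimated date of conception) during the study or within 2 weeks" of the last relugolix dose. For the comparator it adds "3 months after the last dose of leuprolide acetate 22.5 mg 3-M or 6 months after the last 45 mg 6-M depot injection". Collection depends on the partner's signed release. When a pregnancy is reported, the investigator is to inform the sponsor "and should follow the procedures outlined in" Appendix 3. No distinction by arm is made. The section adds that abnormal pregnancy outcomes "are considered serious adverse events".

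Appendix 3 has three bullets on partners who become pregnant:

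- The first says that the CRO or investigator will attempt to collect information on a "female partner who becomes pregnant while the male patient is in this study", and then: "This applies only to male patients who receive relugolix".
- The second gives the reporting times: "The investigator is to report a female partner pregnancy to the CRO within 8 calendar days of awareness", and then from the CRO to the sponsor within 5 days. It states no arm limit.
- The third covers recording once the release is signed, and follow-up of mother and child. It states no arm limit either.

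**The concern.** A site reading Section 8.3.5 would seek information on partner pregnancies in both arms and through the post-dose windows. A site that follows the cross-reference and starts at the first bullet of Appendix 3 would seek it in relugolix patients only. A class of safety information whose abnormal outcomes are serious adverse events could then be gathered differently by arm, and differently between sites.

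Safety is the only remaining objective under Amendment 2 (Section 3). Continuing patients come off study supply by the end of 2024 (Section 4.1), so they pass through the post-dose period during which the two sections differ.

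**Working it through.** No plan figure is involved, so the check is a comparison of the two texts.

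| Regimen | Section 8.3.5 | Appendix 3, first bullet |
|---|---|---|
| Relugolix | During study, plus 2 weeks after last dose | While in the study; no post-dose window stated |
| Leuprolide 22.5 mg | During study, plus 3 months after last dose | Excluded by the arm sentence |
| Leuprolide 45 mg | During study, plus 6 months after last injection | Excluded by the arm sentence |

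**Arm.** Section 8.3.5 gives windows for 3 regimens. The first bullet covers 1 of the 3 and excludes 2. Both statements cannot govern. Nor can Section 8.3.5 be read as relugolix-only, because its two leuprolide windows would then have no purpose.

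**Time.** The bullet is narrower than Section 8.3.5 but does not deny the windows. Its word *only* attaches to the arm. How much of a window falls outside the bullet depends on when a patient stops being in the study, and the protocol gives two markers:

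- Section 4.4 ends the study at the last dispensation. For leuprolide that is the last injection, so the full 3 or 6 months lies beyond it. For relugolix it is the last delivery, so the full 2 weeks after the last dose lies beyond it if that dose is taken on or after the delivery date.
- Section 7.4 uses the last contact: "For an individual patient, study completion is defined as their last study communication at the end of the study". This fixes no date. For relugolix, the uncovered part is 2 weeks minus the time from last dose to last contact, bounded below by 0 and above by 2 weeks. If the contact is on or before the last dose, it is 2 − 0 = 2 weeks. If the contact is 2 weeks or more after the last dose, it is 0.

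For leuprolide the choice of marker does not matter, since the arm sentence already excludes those patients.

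**What still covers leuprolide patients.**

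- Two of the three Appendix 3 bullets (3 − 1 = 2) have no arm limit. A pregnancy known to the investigator is therefore reported, recorded and followed in either arm.
- During participation, both arms complete questionnaires every 3 months (Section 8.2.1). Serious adverse events known to the site go to the sponsor within 24 hours (Section 8.3.1.1). Abnormal outcomes qualify in both arms.
- After participation the cover is passive. Questionnaires stop at transition to standard of care (Section 8.2.1). Investigators need not look for serious adverse events, and must notify the sponsor only of those they learn of and judge reasonably related (Section 8.3.1.1).

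So the gap is the seeking of information in the leuprolide arm, mainly after participation.

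**The case against.** The strongest reply has four parts.

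- *Section 8.3.5 is itself driven by reports.* The patient is asked to report, and Appendix 3 is cited for procedures once a report exists. From then on the second and third bullets apply to both arms. This stands, and it confines the point to the first bullet. A reader might infer that leuprolide partner pregnancies would go unreported or unfollowed; the documents do not support that.
- *The appendix does not contradict the post-dose windows; it fails to repeat them.* This also stands. A reader might take the bullet as barring collection after the last dose, but nothing in it says so. Only the arm sentence is a contradiction.
- *Relugolix-only collection may be what the sponsor meant.* The contraception advice in Appendix 3 concerns relugolix alone, and the stated objective is the safety of relugolix. That intent is possible, but it leaves the leuprolide windows in Section 8.3.5 unexplained. The text gives two answers and the sponsor has to choose one.
- *Nothing in the analysis turns on it.* Correct. Protocol Section 9.1 plans no formal primary or secondary analysis, and the SAP specifies no pregnancy output. An abnormal outcome would appear only among the serious adverse event summaries or listings (SAP Section 6.1).

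**Conclusion.** The concern holds, as a minor inconsistency in safety data collection. The arm limit in the first bullet of Appendix 3 contradicts Section 8.3.5 for 2 of the 3 regimens that have a window. The same bullet leaves out the post-dose windows, which is an omission. The practical effect is that information on leuprolide-arm partner pregnancies may not be sought, mainly after participation, and that sites may differ in this.

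The documents give no number of partner pregnancies. The assumption here is that they are rare, and there may be none. No sample size, error rate or treatment estimate is affected, so an inference of bias in a planned comparison would go too far.

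Table 1 also lists a 42 mg leuprolide emulsion for which Section 8.3.5 gives no window. A reader might count that as part of the same conflict. It is a separate missing detail, since the two sections do not disagree about it.

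**What to change.** Edit the first bullet of Appendix 3 in two places:

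1. Delete the sentence "This applies only to male patients who receive relugolix".
2. In "female partner who becomes pregnant while the male patient is in this study", replace everything from *while* onward with: *during the study or within the post-dose period given in Section 8.3.5*.

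If no further amendment is planned, issue the same rule to sites as a written clarification and reflect it in the safety management plan (Section 8.3.6). If relugolix-only collection is what the sponsor wants, it should say so and remove the leuprolide windows from Section 8.3.5. That also ends the conflict but leaves collection one-sided.

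The text change is confined to one bullet. The cost is in follow-up: for a leuprolide patient, conception may count up to 6 months after the last injection, and the pregnancy is then generally followed to 6 to 8 weeks past the due date, well after the move to standard of care. With few or no events expected, that burden should be small overall, though long for any one case.

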PT	preferred term
SAP	statistical analysis plan
SD	standard deviation

1. INTRODUCTION

This document describes detailed statistical analysis to be conducted for study protocol amendment 2 MVT-601-056 (dated 29 Feb 2024), entitled, “Relugolix Versus Leuprolide in Patients with Prostate Cancer: A Randomized Open-Label Study to Assess Major Adverse Cardiovascular Events (REPLACE-CV).” This Statistical Analysis Plan (SAP) will provide details to further elaborate statistical methods as outlined in the protocol amendment 2 MVT-601-056 as well as analysis conventions to guide the statistical programming work.

This SAP is developed in accordance with the International Council on Harmonisation (ICH) guidelines:

- Food and Drug Administration (FDA) draft guidance (Submitting Documents Using Real-World Data and Real-World Evidence to FDA for Drugs and Biologics, May 2019);
- International Conference on Harmonisation (ICH) guidelines E3 (Structure and Content of Clinical Study Reports) and E9 (Statistical Principles for Clinical Trials);
- ICH E9(R1) (Addendum: Estimands and Sensitivity Analysis in Clinical Trials, May 2021).

All decisions regarding statistical analysis of the study, as defined in this SAP, will be made prior to database lock for interim analysis or unblinding of the study data for final analysis. The SAP is to be finalized and approved by the sponsor before unblinding of the study data or the lock of study database. Any changes to the final SAP (or SAP amendments, if applicable) after the study database lock will be clarified in the clinical study report (CSR) with “change from the planned analysis”.

The study was terminated early by the Sponsor in Nov 2023. The FDA was notified on 01 Dec 2023, and investigative sites were notified on 04 Dec 2023 to stop enrollment.

Analyses will be performed using SAS® version 9.4 or higher (SAS Institute, Inc., Cary, NC 27513).

1.1. Study Objectives and Endpoints

The study objectives are summarized in [Table 1](#).

Table 1: Study Objectives and Endpoints

Objectives	Endpoint
Objective	

To describe the safety of relugolix in the study population	
The safety of relugolix will continue to be assessed in the study population. 
Adverse events (AEs) as characterized by type, frequency, severity, seriousness, and relationship to study drugs

2. STUDY DESIGN

2.1. Summary of Study Design

The original study was a randomized open-label study to evaluate the risk of MACE in patients with prostate cancer with defined high-risk cardiovascular disease who are appropriate to be treated either with relugolix or leuprolide acetate for a planned duration of 12 months or more. This study was terminated by the Sponsor on 01 Dec 2023. In an effort to avoid treatment interruptions, patients who had been enrolled will be allowed to remain on study drug up to a period of 12 months ending Dec 2024 if they choose to remain in the discontinuation phase of the study. During this discontinuation phase, all active investigative sites will be expected to formulate a transition plan for their study patients from this clinical study to standard of care (SoC) as soon as practicable.

The study population includes men ages 18 and older with prostate cancer. Deviations from inclusion and exclusion criteria are not allowed. Eligibility criteria are described below.

Inclusion Criteria:

1. Was previously enrolled in the original version and amendment 1 of this study
2. Has voluntarily resigned and dated the informed consent form prior to transition to the discontinuation phase of this study

[figure not shown]
Exclusion Criteria:

Not applicable as patients were previously excluded under the original version and amendment 1.

Disclosure Statement:

This is a randomized study with collection of clinical data at baseline and at follow-up.

Figure 1: Study Schema

Abbreviations: ADT = androgen deprivation therapy; ER = emergency room; MACE = major adverse cardiovascular event; PSA = prostate-specific antigen; R = randomization.

2.2. Sample Size Considerations

The original study is an event-driven study. A two-stage group-sequential design is considered in the study. The type-I error is controlled by the α -spending methodology of Lan and DeMets (1983). The upfront estimated total sample size of the study is approximately 2250 patients (from whom a target total of 237 events [ie, 237 patients who have events] are to be observed) to achieve 90% power for the target hazard ratio of 0.65 at a two-sided significance level (alpha) of 0.05. The study is adequately powered to detect clinically meaningful treatment effect (target hazard ratio [HR] = 0.65) and will be monitored at 60% (information fraction, 142 events [ie, 142 patients who have events]) with the possibility of early termination if there is overwhelming evidence of efficacy or futility. The following assumptions are considered: percentage of patients remaining event-free at one-year in the leuprolide acetate group is 93.5% (ie, MACE rate at one-year is 6.5%), about 96% in the relugolix group (ie, MACE rate at one-year is about 4%) and dropout rate is 5% at one-year for either relugolix group or leuprolide acetate group. A constant hazard ratio is assumed throughout the study and a stratified log-rank test and Cox proportional hazards model are used to analyze the data

As of 04 Dec 2023, study was terminated and enrollment into the study was stopped.

3. PLANNED ANALYSES

For the original study of group-sequential (G-S) design study, there are two planned analyses (one formal interim analysis and a final analysis).

As of 04 Dec 2023, study was terminated and no formal efficacy statistical analyses will be performed but safety analyses will be performed.

4. GENERAL CONSIDERATIONS FOR DATA ANALYSES AND HANDLING OF MISSING DATA

4.1. Data Presentation Conventions

All statistical analyses will be conducted using SAS® Version 9.4 or higher.

Statistical tests for the primary and secondary endpoints will be assessed at a two-sided $\alpha = 0.05$ significance level, and all confidence intervals will be reported as two-sided, unless otherwise stated.

Where appropriate, variables will be summarized descriptively by study visit. For the categorical variables, the count and proportions of each possible value will be tabulated by treatment group. For continuous variables, the number of patients with non-missing values, mean, median, standard deviation (SD), minimum, and maximum values will be tabulated.

4.2. Analysis Populations

As of Dec 2023, only safety population will be analyzed.

4.2.1. Safety Population

Safety population is defined as all randomized patients who are treated with at least one dose of relugolix or one injection of leuprolide after the date of randomization to the study. Safety population will be used to analyze other safety data including treatment-emergent serious adverse events and clinical laboratory tests as obtained per standard of care.

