Patients will be randomized 1:1 for this study to either relugolix or to leuprolide acetate using permuted block randomization.

As of 04 Dec 2023, patients currently enrolled in this study will be provided with up to a 12-month clinical supply of the randomized study intervention (relugolix or leuprolide acetate) they had been previously assigned. This supply will allow for transition from study treatment to SOC by their health care providers as soon as practicable.

Statistical Methods

Analysis Population

[figure not shown]
The analysis population is the Safety Population defined as all patients who are randomized into the study with at least 1 dose of study drug.

Sample Size Estimation

As of 04 Dec 2023, enrollment into the study was stopped and no formal statistical analysis will be performed.

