1.3. Schedule of Activities

NOTE: During the discontinuation phase of the study, questionnaires will be collected until early termination/end of study to collect safety information. Other assessments may be performed at the discretion of the Investigator.

Assessment/Procedure	Responsible Party	Screening ^a (28 days before Day 1)	Day 1	Study Treatment Period ^b (Months)					Early Termination/ End of Study ^c
				3	6	9	12	Every 3 Months	
Informed consent	Investigator	X							
Inclusion and exclusion criteria	Investigator	X							
Demographics	Investigator	X							
Physical examination ^d	Investigator	X							
Vital signs ^e	Investigator	X							
Weight and height ^f	Investigator	X							
12-lead ECG	Recruiting physician (if not done within 6 months prior to screening, see Section 8.2.1.3)	X							
Medical history (including detailed prostate cancer history, current prostate cancer disease status and treatment at study entry)	Patient-reported (Baseline questionnaire)	X							
	Recruiting physician								
Family history of cardiovascular disease	Patient-reported (Baseline questionnaire)	X							

Protocol Amendment 2

Assessment/Procedure	Responsible Party	Screening ^a (28 days before Day 1)	Day 1	Study Treatment Period ^b (Months)					Early Termination/ End of Study ^c
				3	6	9	12	Every 3 Months	
Testosterone	Investigator (if not done within 6 months prior to screening, see Section 8.2.1.4)	X							
	Investigator			6 weeks after start of study treatment, every 6 months thereafter, and at time of PSA rise (Section 8.2.1.4).					
Serum PSA	Investigator (if not done within 6 months prior to screening, see Section 8.2.1.4)	X							
Baseline questionnaire	Patient-reported	X							
PROMIS Short Form V2.0 – Cognitive Function 8a ^g	Patient-reported	X		Every 12 months on study.					
Randomization	Investigator		X						
Study intervention administration: leuprolide acetate or relugolix ^h	Investigator		X ⁱ	Administered as per label.					
Standard of care visit ^j	Investigator			X	X	X	X	X	X ^c
Follow-up questionnaires ^k	Patient-reported			X	X	X	X	X	X
Early discontinuation / End of study questionnaire	Patient-reported								X

Protocol Amendment 2

Assessment/Procedure	Responsible Party	Screening ^a (28 days before Day 1)	Day 1	Study Treatment Period ^b (Months)					Early Termination/ End of Study ^c
				3	6	9	12	Every 3 Months	
Selective safety data ^l	Patient-reported (Follow-up questionnaire)	X		X	X	X	X	X	X
	Investigator		X (see Section 8.3)						

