Concomitant medications ^m	Investigator	X							
	Patient-reported (Follow-up questionnaire)	Patient-reported		X	X	X	X	X	
Drug accountability	Clinical trial supply vendor (or designee)			X	X	X	X	X	X

Abbreviations: CRO = clinical research organization; ECG = electrocardiogram; eCRF = electronic case report form; PSA = prostate-specific antigen.

^a Recruiting and screening will be completed by the study centers. Study centers will educate, set the study expectations, and obtain informed consent from study patients. Informed consent forms will include permission for study data to be collected, analyzed, and for contacts to be made by the CRO study team at specific time-intervals during follow-up for the collection of study information. Each patient will also be asked to provide information regarding alternative contacts (eg, close relatives or friends, or primary care physician or cardiologist). If the CRO cannot reach the patient or relatives after several attempts, they will contact the patient's primary care physician/cardiologists/attending physician(s).

^b Patient's responses will be collected (every 3 months) via an electronic questionnaire (or phone calls or other methods if the patient and family member are unable to complete the questionnaire electronically). The questionnaires will be collected until the end of study. Patients will be instructed to consult with the principal investigator if they do not have access to a phone or an electronic device. Note: Other assessments may be performed (in clinic or telehealth) per investigator's discretion during the discontinuation phase of study, but are no longer required.

^c Can be performed in clinic or telehealth as standard of care begins.

^d A complete physical examination will be performed (see Section 8.2.1.1).

^e Vital signs will be measured in a seated position after 5 minutes rest and will include oral temperature, pulse rate, and systolic and diastolic blood pressure. Two readings of blood pressure will be taken and averaged.

^f Body mass index will be calculated based on weight and height.

^g Potential decline in cognitive function as seen on follow-up will be discussed by the medical monitor and investigator.

^h Relugolix will be mailed to patients.

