Despite the literature evidence available in the last years from different type of studies (randomized controlled, observational, and meta-analyses), GnRH receptor agonists remain the standard of care for men requiring androgen deprivation therapy (ADT) for advanced prostate cancer. Furthermore, although guidelines on use of ADT in prostate cancer do highlight the need for screening and intervention to prevent/treat diabetes and cardiovascular disease, there is no recommendation for any particular type or class of ADT ([Schaeffer et al. 2021](#)). Currently GnRH receptor agonists are the standard of care. One major disadvantage of using an agonist to suppress testosterone is the initial stimulation of the hypothalamus-pituitary-gonadal axis that occurs prior to desensitization and lasts 1 to 3 weeks. This results in a rise in luteinizing hormone and follicle stimulating hormone, a subsequent testosterone surge, and in some men, an increase in clinical symptoms ([Oh et al. 2010](#)), including increased bone pain, spinal cord compression, pathologic fracture, bladder outlet obstruction, and even death ([Oh et al. 2010](#)). Cardiovascular events also have emerged as an immediate post-treatment concern with GnRH agonists, perhaps due to the hormone surge ([Margel et al. 2019](#); [Shore 2020](#)).

Since 2010, the Food and Drug Administration (FDA) has required that the risk of cardiovascular disease be included in the safety information for GnRH receptor agonists. Eligard® and Lupron Depot® labeling include a warning of an increased risk of myocardial

infarction, sudden cardiac death, and stroke associated with use of GnRH receptor agonists in men and recommend that patients be monitored for symptoms and signs suggestive of development of cardiovascular disease (Eligard USPI 2019; Lupron Prescribing Information 2019). The increased risk associated with the use of GnRH receptor agonists is hypothesized to occur in two distinct timeframes. An early increase in cardiovascular risk has been described in men with preexisting cardiovascular disease, possibly from plaque rupture and resultant thrombosis, whereas a later increase in risk may occur from the resulting hypogonadal state with an increase in central obesity, insulin resistance, hypertension, and hyperlipidemia (Albertsen et al. 2014; Crawford et al. 2017; Margel et al. 2019).

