6.3. Randomization and Stratification

Eligible patients were assigned to one of two treatment groups in accordance with the randomization schedule using an Interactive Response Technology System. At baseline prior to the start of study intervention administration, each patient was randomized in Interactive Response Technology in a 1:1 ratio to one of 2 treatment groups (see [Table 2](#)).

Table 2: MVT-601-056 Treatment Arms

Treatment Arm	Randomized Treatment
Group A	Relugolix 360 mg (three 120 mg tablets) single oral loading dose on Day 1 followed by 120 mg orally once daily
Group B	Leuprolide acetate, 22.5 mg 3-M depot injection or Leuprolide acetate, 45 mg 6-M depot injection

Randomization was centrally stratified by the following factors using a permuted block method (see Section [4.1](#) for further details on the factors):

- MACE history (yes versus no);
- Age (≤ 65 versus > 65 years old);
- Presence of metastatic prostate cancer (yes versus no) (metastases in regional lymph node[s] are considered N1 and will, therefore, be stratified as non-metastatic).

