9.2. Analysis Populations

Safety population is defined as all randomized patients who are treated with at least one dose of relugolix or one injection of leuprolide acetate after the date of randomization to the study.

Safety population will be used to analyze other safety data including treatment-emergent adverse events and clinical laboratory tests as obtained per standard of care.

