4.3.2. Study Day

Study day will be calculated with respect to the date of randomization (Study Day 1). For assessments conducted on or after the date of randomization, study day will be calculated as:

$$(\text{Assessment date} - \text{date of randomization}) + 1$$

For assessments conducted before the date of the randomization, study day will be calculated as:

$$(\text{Assessment date} - \text{date of randomization})$$

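### Read literally, the Safety Population rule leaves out leuprolide patients injected on the randomization date until a second depot injection, and it conflicts with the protocol synopsis

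*SAP*

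**What the plan says.** The documents define the Safety Population three times.

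- SAP 4.2.1: "all randomized patients who are treated with at least one dose of relugolix or one injection of leuprolide after the date of randomization".
- Protocol 9.2: randomized patients "treated with at least one dose of relugolix or one injection of leuprolide acetate after the date of randomization to the study".
- Protocol synopsis (1.1): "all patients who are randomized into the study with at least 1 dose of study drug". There is no date condition.

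On timing, the Schedule of Activities (Protocol 1.3) has a row "Study intervention administration: leuprolide acetate or relugolix" marked in the Day 1 column, the same column as randomization. SAP 4.3.2 makes the randomization date Study Day 1. Protocol 6.3 gives the order of events: "At baseline prior to the start of study intervention administration, each patient was randomized". It does not require the two to fall on different calendar days.

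On supply and interval, a footnote to the Schedule says "Relugolix will be mailed to patients", and the drug is then taken daily. Leuprolide is sourced by the site and given as a 3-month or 6-month depot (Protocol 6.1).

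SAP 4.2 says that only the Safety Population will be analyzed, and describing safety is the sole remaining objective (Protocol 3, SAP 1.1).

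**The concern.** A condition of dosing strictly later than the randomization date works differently in the two arms. For a daily tablet it costs at most one day. For a depot injected on the day of randomization it postpones entry to the second injection, months later. Membership of the leuprolide column would then depend on what happens to the patient after treatment starts, which is a form of immortal-time selection.

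The patients at risk of being left out are those who die, withdraw, stop because of an adverse event or move to standard of care after a single Day 1 injection. Serious adverse events and adverse events leading to discontinuation are what this trial collects (Protocol 8.2). Treatment-emergent serious events count from the first dose (SAP 6.1), so these events would otherwise be tabulated. Losing them would make leuprolide look safer on deaths and treatment-ending events. A patient who leaves without an event is lost from the denominator only, which pushes the other way, so the net direction for other rows is not fixed.

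**Working it through.** The plan states no figure for this point. The 237-event target in SAP 2.2 belongs to the abandoned comparison and is not involved.

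**Step 1: date logic.** Let R be the randomization date. The rule in SAP 4.2.1, as written, needs at least one dose date later than R.

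| Patient | First dose | First date that satisfies the rule |
|---|---|---|
| Leuprolide, injected on R | R | Second injection, about 3 or 6 months later |
| Leuprolide, injected after R | after R | First injection |
| Relugolix, started on R | R | Day 2 |
| Relugolix, started after R (tablets arrive by mail) | after R | First dose |

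The literal reading is not forced. In SAP 4.3.2 the authors write *on or after* when they mean to include the randomization date; in 4.2.1 they do not. A programmer could reasonably code a strict inequality. A leuprolide patient injected on R would then have a valid first-dose date under SAP 4.3.1 and a treatment-emergent window under SAP 6.1, yet fail the population rule.

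**Step 2: share of Day-1-injected leuprolide patients excluded.**

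Input from the documents: dropout of 5% at one year in either arm (SAP 2.2). This is a yearly proportion, so for m months the share lost is 1 − (1 − 0.05)^(m/12).

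- 3-month depot: 1 − 0.95^0.25 = 1.3%
- 6-month depot: 1 − 0.95^0.5 = 2.5%

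The SAP does not say whether that 5% includes deaths, so it is a starting point and not a ceiling.

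Assumed input: a combined yearly rate r of death or stopping of 0.10 to 0.20, which is not in the documents. With a constant hazard the share lost is 1 − exp(−r·m/12).

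| r | 3-month depot | 6-month depot |
|---|---|---|
| 0.10 | 2.5% | 4.9% |
| 0.20 | 4.9% | 9.5% |

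If 10% and 20% are taken as yearly proportions instead, the results are 2.6% and 5.4% (3-month) or 5.1% and 10.6% (6-month).

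**Step 3: from Day-1-injected patients to the arm.** The share q of leuprolide patients injected on the randomization date is not stated, so the figures in Step 2 must be multiplied by q. At 5% dropout, per 1000 leuprolide patients:

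| q (assumed) | 3-month depot | 6-month depot |
|---|---|---|
| 0.25 | 3.2 | 6.3 |
| 0.5 | 6.4 | 12.7 |
| 1 | 12.7 | 25.3 |

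**Step 4: after the correction.** If the rule includes the randomization date, every Day-1-injected patient enters and the share excluded for this reason is 0%.

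**The case against.** The best answer is that the intended meaning is plainly a dose given after randomization, not after that calendar day. Protocol 6.3 puts randomization before dosing, SAP 4.3.1 accepts the injection visit as first dose with no date exclusion, and the synopsis would include these patients. That is probably right about intent. It does not remove the conflict, because the restrictive wording is the one in the SAP and a program follows the wording.

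It is also fair that the Day 1 column covers relugolix as well as leuprolide, so Day 1 may be nominal for both. The documents allow a same-day injection without showing how often it occurred.

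Little inference remains to be biased. Protocol 9.1 and SAP 3 rule out formal primary, secondary and efficacy analyses, and the stated objective concerns relugolix, whose arm is hardly affected. SAP 6.1 promises a listing of all serious adverse events, and SAP 4.4 summarizes disposition on an ITT population, so the excluded patients need not vanish from the report. These points stand and limit the harm to the descriptive leuprolide columns.

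A reader might go further in three ways that the documents do not support.

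- That a stated percentage of the whole leuprolide arm is lost. This would require every patient to be injected on the randomization date.
- That everyone with one injection before the December 2023 stop is lost too. Enrollment stopped then. Enrolled patients could stay on assigned drug for up to 12 months, so a second injection remained possible unless they left or moved to standard of care first.
- That the excluded window is where the protocol expects agonist cardiovascular risk to be concentrated. Protocol 2.1 does say "An early increase in cardiovascular risk has been described in men with preexisting cardiovascular disease", but the same sentence goes on to a later increase as well.

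**Conclusion.** The inconsistency is real and should be corrected, but it is a low-cost wording repair and not a flaw that undermines the study. Two sections carry a date condition that the synopsis lacks. Under a literal reading, that condition selects leuprolide patients on survival and continued treatment while barely touching relugolix patients.

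The size is modest and uncertain: about 1.3% or 2.5% of Day-1-injected leuprolide patients at the SAP's own dropout figure, and up to 9.5% at the top of the assumed hazard range with the 6-month depot. All of these are scaled down by the unknown share injected on Day 1. The loss matters more than its size suggests because it falls on deaths and treatment-ending events in one arm. The conclusion rests on the rule being programmed as written, on some leuprolide patients having been injected on the randomization date, and on a constant loss rate up to the second injection.

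**What to change.** Before database lock, change SAP 4.2.1 to: *all randomized patients who received at least one dose of study drug on or after the date of randomization*. Bring Protocol 9.2 and the synopsis to the same definition at the next amendment, or state in the SAP that this definition governs. The new text keeps a date condition that the synopsis lacks. Because Protocol 6.3 has randomization precede dosing, both should select the same patients, but the wording should still be made identical.

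It would help to count, by arm, the patients whose only dose date equals the randomization date. That would replace the ranges above with a number.

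The SAP change is one phrase. No new data are needed: leuprolide injection dates and the relugolix start date are already recorded in the electronic data capture system (Schedule of Activities footnotes). A protocol amendment needs IRB/IEC approval (Protocol Appendix 1), so the SAP clarification is the cheaper route if no amendment is otherwise planned.
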